### Phase 3: Data Analysis and Dissemination

The objectives of this phase are 1) to conduct data analysis and 2) to disseminate the program.

In Year 5, we will complete post-intervention assessments, data analyses and report writing.

Process and outcome data will be presented at scientific conferences and manuscripts will be submitted to peer-reviewed scientific journals. Ultimately, we envision that **I-ANBL**, if efficacious, could be disseminated and

used as a culturally tailored smoking cessation intervention that could be adopted across different tribal colleges.

**Sample Size and Power:** The primary endpoint will be cotinine verified 7-day point prevalence abstinence at Month 6. Per preliminary findings, we expect a 30% cessation rate in the **I-ANBL** arm and a 15% cessation rate in the **I-FV** arm. Using the chi-square test, and the assumptions above, 121 participants in each group will give us 80% power to detect this difference with a type I error rate of 5%.

Given retention rates from our earlier studies, we expect attrition rates to be approximately 20% over the 6 month study period. Therefore, we anticipate needing to enroll 300 participants at baseline in order to have 242 active participants at 6 months.

### **Statistical Analyses:**

We will first summarize all baseline measures globally and by treatment group. Categorical variables will be presented by frequencies and percentages within each of the possible categories and quantitative variables will be presented by means and standard deviations. Then, generalized linear modeling and mixed modeling will be applied to hypothesis testing for the primary and secondary aims (see below). In addition, for the exploratory purpose, we will evaluate potential covariates including smoking history and demographic, psychological, and sociocultural factors that may contribute to smoking abstinence. Interactions between intervention and these factors will also be investigated (i.e., moderation). All analyses will be conducted using SAS 9.2.

### **Primary Aim/Hypotheses:**

1. To test the effectiveness of the **I-ANBL** compared to the **I-FV** on smoking cessation among tribal college smokers.

Hypothesis 1: At 6 months, participants in the **I-ANBL** group will show higher 7-day point prevalence abstinence rates than those in the **I-FV** group.

We will compare the salivary cotinine verified prevalence abstinence rates at 6 months between the two groups using logistic regression. For our primary comparison, we will conduct per-protocol analyses on (a) only the participants who complete the study, as well as intent-to-treat analyses on (b) all subjects by imputing the dropouts as smokers and (c) all subjects by using the Markov Chain Monte Carlo (MCMC) imputation technique. In (c), the missing data related to attrition can be reasonably assumed to be missing due to known characteristics of our database (i.e., missing at random). We will create a large number of (e.g., 200) complete datasets via expectation-maximization algorithm as prior estimates for the MCMC procedure; and then combine the analysis outcomes from each complete dataset to make valid statistical inferences. To evaluate secondary endpoint, we will compare the salivary cotinine verified prevalence abstinence rates between the groups at Week 12 (end of pharmacotherapy). Finally, as we have no preliminary estimates of relapse based upon timeline follow-back, we will conduct explanatory, failure analyses to compare the time to relapse between the groups. We will calculate failure function (cumulative probability of smoking cessation as a function of time) and fit Cox regression models to the 6-month self-report data on smoking status.

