### **Formative Research for this Proposed Study**

Our American Lung Association (ALA) funded (SB-11343-N, PI: [name]) formative research addressed the important and neglected public health problem of smoking among AI/ANs. The goal of this project was to identify culturally acceptable and potentially effective methods for smoking cessation in this underserved and high risk population.

**Focus Groups:** We conducted six focus groups with AI/AN smokers (N=41) at HHC to determine facilitators and barriers to smoking cessation, and the feasibility of developing a smoking cessation program for a heterogeneous AI/AN population. These participants represented 23 different nations.

Participants discussed three major themes: traditional use of tobacco, quitting and quit attempts, and smoking cessation program. We currently have two published manuscripts (see appendix) and two national presentations based on these data. Based on results of these focus groups and meetings with AI/AN community members, we began creation of a culturally-tailored smoking cessation program.

**Feasibility/Compliance Pilot:** Based on the findings from our focus groups, previous smoking cessation programs developed by members of our team, and the Second Wind program, we began creation of the ANBL program. The pilot version was developed with direct community involvement in an iterative process that included weekly meetings with AI/AN colleagues and community members. It included group sessions and individual phone calls, but used different timing and frequency, as well as a draft curriculum. The name, “All Nations Breath of Life” and slogan, “Light Up a New Way,” were selected from community members’ submissions to a contest. We completed a pilot project to test the implementation feasibility and participant compliance of ANBL at HHC with 30 AI/AN smokers. All participants were offered either nicotine patch or bupropion for free. At the end of the 12 week program, 80% of our participants were smoke free. At 6 months, approximately 25% of the participants remained abstinent (verified through carbon monoxide test). At 6 months, our retention rate was approximately 80% for this pilot. During our pilot studies, we collected data on the characteristics of smokers at HHC.

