#### **Pilot Feasibility of ANBL in Urban and Reservation based Tribes in Kansas**

Our American Cancer Society (RSGT-06-260-01-CPPB: PI: [name]) funded grant is a 3 year pilot/feasibility study of ANBL with all program components. The ANBL program components include an initial individual session along with 8 weekly group sessions with individual telephone calls between the group sessions. During the previous pilot, we conducted the ANBL program with 5 weekly in person sessions and another version with 8 weekly in person sessions. The overwhelming preference from our participants was for the more intensive 8 weekly in-person group sessions. All of our participants expressed the need to maintain the group support and dynamics in order to maintain long term abstinence. As a result, we decided to implement the 8 session version rather than the smaller number of sessions. This larger pilot study started in 2006 and we have completed 10 groups of AI/AN smokers. In addition to the ANBL program, all participants were offered varenicline as a form of pharmacotherapy. In this pilot, we also added the use of motivational interviewing (MI) counseling throughout the individual phone sessions. Recruitment and retention (approximately 80%) has been very successful. All participants completed surveys for each group session and there have been no refusals among those in attendance. For the first time, we have also collected saliva samples from our participants at baseline, week 12 and 6 months to verify smoking status. The six month smoking abstinence rates are approximately 30% with ANBL in combination with varenicline. Our dropout rates for this larger feasibility pilot study have been between 15-20 % at 6 months.

***These results demonstrate our team's ability to recruit both urban and reservation based AI/AN smokers in the region. In addition, we have successfully shown our team's ability to maintain high recruitment and retention rates for the groups of smokers for the high intensity ANBL program. We have also successfully integrated the use of MI counseling during the individual phone calls and demonstrated acceptance in this population. Our current version of ANBL is more intense compared to the first version of the program. This increase in intensity is a result of participant and facilitator feedback that 5 in-person group sessions was***

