### **Secondary Aims/Hypotheses:**

1. To test the effects of the intervention on intermediate smoking variables including number of cigarettes smoked and number of quit attempts at 6 months following randomization.

Hypothesis 1A: At 6 months following randomization, among those who continue to smoke, participants in the

**I-ANBL** group will show a greater reduction in the number of cigarettes smoked than participants in the **I-FV** group. Mixed models for repeated measures will be used to examine the change in the number of cigarettes smoked over the 6-month study period. To evaluate group differences of reduced cigarette numbers, the models will examine the main effects of time, treatment, and the number of cigarettes smoked at baseline and their interactions. Estimated means at 6 months, which are adjusted for the baseline cigarette numbers, will be reported and compared between the groups.

Hypothesis 1B: Smokers receiving I-ANBL will make greater number of serious quit attempts than smokers receiving I-FV. We will compare the number of quit attempts between the two groups using Poisson regression for count data. In the Secondary Aim 1 analyses, the dropouts will be handled by multiple imputation as described in Primary Aim.

2. To compare differences between **I-ANBL** and **I-FV** in adherence rates to program participation at 6 months following randomization.

Hypothesis 2: At 6 months following randomization, participants in the I-ANBL group will have significantly higher adherence rates than smokers in the **I-FV** group.

We will summarize and compare the measures of program exposure and dose between the groups by descriptive statistics and the *t*-test or chi-square test. Then, we will examine group differences in adherence rates by modeling the binary outcome (dropouts vs. completers) with logistic regression.

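### Three analyses of the 6-month abstinence endpoint all carry the primary label, with no ranking and no rule if they disagree

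*Protocol*

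**What the plan says.** Protocol section V, Phase 3, under Primary Aim/Hypotheses, has one primary hypothesis: higher cotinine-verified 7-day abstinence at 6 months in I-ANBL than in I-FV, compared by logistic regression. Three analyses then follow under one label:

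- (a) "For our primary comparison, we will conduct per-protocol analyses on (a) only the participants who complete the study";
- (b) "all subjects by imputing the dropouts as smokers";
- (c) "all subjects by using the Markov Chain Monte Carlo (MCMC) imputation technique".

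The text calls (b) and (c) intent-to-treat and joins them to (a) on an equal footing. None is called main, supportive or sensitivity, here or elsewhere in the protocol.

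Sample Size and Power, earlier in Phase 3, assumes abstinence of 30% and 15% and states that "121 participants in each group will give us 80% power to detect this difference with a type I error rate of 5"%. It adds that "we expect attrition rates to be approximately 20% over the 6 month study period", and so plans 300 enrolled to keep 242 at 6 months. It does not say whether 30% and 15% are rates among completers or among everyone randomised.

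**The concern.** One hypothesis with three primary analyses needs a decision rule, and there is none. If the results split, the protocol cannot say whether Hypothesis 1 was met, and whoever reports the trial can choose. The analysis listed first, completers only, also does not preserve the randomised groups.

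The quoted error rate and power belong to one test on 121 per group, which is the completer set. They do not carry over to an any-of-three or an all-of-three rule.

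The three analyses diverge most when dropout differs by arm. The protocol allows for that: Hypothesis 2 under Secondary Aims expects higher adherence in I-ANBL, and "we will examine group differences in adherence rates by modeling the binary outcome (dropouts vs. completers) with logistic regression".

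**Working it through.** **Inputs from the protocol.** 150 per arm; 30% vs 15%; 121 per group; 5% error; 80% power; about 20% attrition with no split by arm. Sidedness is not stated, but two-sided reproduces the sample size.

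**The plan's own figure.** Pooled two-proportion formula with p̄ = 0.225:

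n = [1.96·√(2·0.225·0.775) + 0.842·√(0.30·0.70 + 0.15·0.85)]² / 0.15² = 120.5, so 121 per group.

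Power at 121: (0.15·√121 − 1.96·0.5906)/0.5809 = 0.848, giving 80.2%. The figure reproduces.

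**Power depends on which analysis decides.** Same formula:

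| Analysis | 30%/15% are completer rates | 30%/15% already count dropouts as smokers |
|---|---|---|
| (a), 121 per arm | 30% vs 15%: 80.2% | 0.30/0.8 = 37.5% vs 0.15/0.8 = 18.75%: 90.5% |
| (b), 150 per arm | 0.8·30% = 24% vs 0.8·15% = 12%: 77.5% | 30% vs 15%: 87.9% |

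The protocol does not say which column applies. Its pilot results do not settle it: "At 6 months, approximately 25% of the participants remained abstinent" and "The six month smoking abstinence rates are approximately 30% with ANBL in combination with varenicline" are given without saying how dropouts were counted. By simulation, with 20% dropout per arm and completer rates, (c) has about 79–82% power depending on the imputation model. Requiring all three to be significant gives about 75–76%.

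**Split results at 20% overall dropout (60 of 300).** Wald test from logistic regression: z = [ln(x₁/(n₁−x₁)) − ln(x₂/(n₂−x₂))] / √(1/x₁ + 1/(n₁−x₁) + 1/x₂ + 1/(n₂−x₂)).

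*More dropout in I-ANBL* (37 vs 23; 31 and 19 abstinent):
- (a) 31/113 vs 19/127: z = 0.765/0.326 = 2.35, p = 0.019.
- (b) 31/150 vs 19/150: z = 0.586/0.318 = 1.84, p = 0.065.
- (c) multiple imputation without covariates: p = 0.019.

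*More dropout in I-FV, the direction Hypothesis 2 expects* (23 vs 37; 32 and 18 abstinent):
- (a) 32/127 vs 18/113: z = 0.575/0.328 = 1.75, p = 0.080.
- (b) 32/150 vs 18/150: z = 0.688/0.321 = 2.14, p = 0.032.

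So the verdict can turn on the choice in either direction.

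**Type I error by simulation.** 20,000 trials per scenario, 150 per arm, two-sided 5%; pooled z-test for (a) and (b); 200 within-arm imputations combined by Rubin's rules for (c). True abstinence equal in both arms at 15%, 20% or 22.5% (assumed).

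| Dropout | Any one significant | All three significant |
|---|---|---|
| 20% in each arm | 5.8–6.3% | 3.4–4.1% |
| 15% and 25%, either way (assumed) | 8.6–11.8% | 2.6–3.3% |

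A separate simulation that imputed from an assumed week-12 status gave 5.9–7.0% for any one significant with equal 20% dropout, and about 9% at 15%/25%.

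**Multiplicity or bias?** With unequal dropout, most of the excess is bias in a single analysis. Take true abstinence of 20% in both arms and dropout of 15% and 25%. If dropout is unrelated to smoking, (b) sees 0.85·20% = 17% vs 0.75·20% = 15%. If all dropouts smoke, (a) sees 20%/0.85 = 23.5% vs 20%/0.75 = 26.7%. The simulated error is 6.9–8.0% for (b) alone in the first case. In the second it is 7.8–9.7% for (a) alone and 7.4–9.5% for (c) alone.

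**Disagreement at 30% vs 15%.** Share of trials in which the three differ on significance:

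- equal 20% dropout: 6.2% (4.6% if 30%/15% already count dropouts as smokers; about 9.5% with week-12 imputation);
- 15% I-ANBL / 25% I-FV: 11–13%;
- 25% I-ANBL / 15% I-FV: 19.9% (8.7% if 30%/15% already count dropouts as smokers).

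**The case against.** The ranking of missing-data analyses is often settled in an SAP, and one may exist that was not available here. On a mild reading, the protocol has one hypothesis, endpoint, time point and model, and commits in advance to three treatments of dropout. Nowhere does it say that one significant result suffices. On the protocol's own 20% attrition, the any-of-three error is only about 6%, and an all-of-three rule is conservative. The larger figures need an assumed dropout split and mostly reflect bias that naming a primary analysis would not remove. The largest disagreement figure, 19.9%, uses the opposite dropout direction to the one Hypothesis 2 expects.

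The points about size stand: the inflation with equal dropout is about one percentage point, and the larger numbers should not be read as multiplicity alone. The SAP argument does not dispose of the point. The protocol does not leave the choice open; it gives all three the primary label, and an SAP that ranked them would have to depart from that text. Fixing three analyses in advance also supplies no rule for combining them. In the direction Hypothesis 2 expects, the analyses still disagree in 11–13% of trials at 15%/25% dropout.

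**Conclusion.** The concern holds and should be fixed. The primary comparison contains three unranked analyses, and the stated 5% error and 80% power apply to only one of them. The error is somewhat above 5% under an any-of-three rule and below it under all-of-three; in the second case, power is about 75–76% if 30%/15% are completer rates. The sample size of 121 per group is not in error.

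The textual point needs no assumptions. The simulated sizes rest on the assumed null rates and dropout splits and on a simplified version of (c). The planned MCMC could draw on baseline and weekly smoking data, so the figures involving (c) are approximate.

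**What to change.** In Primary Aim/Hypotheses, name either (b) or (c) as the only confirmatory test of Hypothesis 1 at two-sided 5%, fixed before month-6 outcomes are seen by arm. The choice is the sponsor's: either can be biased when dropout is unequal, in a direction that depends on which arm loses more and whether those lost are smoking. Label the other all-randomised analysis and the completers-only analysis as sensitivity analyses that do not change the verdict.

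In Sample Size and Power, state which population the 30% and 15% describe and give the power of the chosen analysis. For (b) that is about 77% if they are completer rates, or about 88% if dropouts already count as smokers.

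Because naming a primary does not cure bias from unequal dropout, also add a tipping-point analysis. It would vary abstinence among dropouts separately by arm, from 0 up to that arm's completer rate. This goes beyond the minimum needed to settle the ranking.

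The cost is wording in two sections and one extra sensitivity analysis, with no added participants or visits.

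### The MCMC imputation described most naturally reads as a normal model, yet it serves a yes/no endpoint and a count; the protocol gives no imputation model suited to either and no conversion rule

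*Protocol*

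**What the plan says.** Under Sample Size and Power the protocol makes the primary endpoint binary: "The primary endpoint will be cotinine verified 7-day point prevalence abstinence at Month 6". Under Primary Aim/Hypotheses the model is also fixed: "We will compare the salivary cotinine verified prevalence abstinence rates at 6 months between the two groups using logistic regression".

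That section lists three analyses for the primary comparison:

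- (a) completers only;
- (b) "all subjects by imputing the dropouts as smokers";
- (c) "all subjects by using the Markov Chain Monte Carlo (MCMC) imputation technique".

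For (c) it adds that a large number of completed datasets (200 is the example) will be created "via expectation-maximization algorithm as prior estimates for the MCMC procedure", and that attrition can be taken as "missing due to known characteristics of our database (i.e., missing at random"). Under Statistical Analyses: "All analyses will be conducted using SAS 9.2".

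Under Secondary Aims/Hypotheses, quit attempts (Hypothesis 1B) are compared by Poisson regression, and number of cigarettes (Hypothesis 1A) by mixed models for repeated measures. For the Secondary Aim 1 analyses, "the dropouts will be handled by multiple imputation as described in Primary Aim". No other handling of dropouts is given there.

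The protocol does not name the imputation distribution. It also gives no rule for turning imputed values into yes/no values or counts.

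**The concern.** The imputation method is partly specified rather than left open: EM estimates feed an MCMC chain, many completed datasets follow, and one software package is named. That is the usual description of imputation under a multivariate-normal model. Such a model draws continuous values. For a yes/no variable they can be fractions, below 0 or above 1; for a count they can be negative or non-integer.

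The stated analysis models are logistic and Poisson. A logistic model for a yes/no outcome cannot take such draws unconverted. A Poisson likelihood is not defined for negative values. Following the text would therefore force someone to round, truncate or drop values, by a rule chosen outside the protocol and possibly after the data have been seen. With 20% attrition expected, about one outcome in five in each arm would be affected in analysis (c) and in the quit-attempt analysis.

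**Working it through.** **Inputs from the protocol.** Abstinence 30% (I-ANBL) and 15% (I-FV); 121 per group for 80% power at a 5% type I error rate; 300 enrolled; attrition about 20% (Sample Size and Power). Allocation 150 and 150 (Anticipated Flow of Participants).

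**Assumptions.** The imputation model is normal. Quit attempts have mean 1 to 2 and variance 1 to 3 times the mean, because the protocol gives neither.

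**The plan's own figure.** For 30% against 15%, two-sided 5%, 80% power, without continuity correction, the required number is 120.5, rounded up to 121 per group (power 0.802). This agrees with the protocol. Inflating 242 for 20% attrition gives 242/0.8 = 302.5, or 303, close to the stated 300. The point below does not change the sample size.

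**Abstinence.** Treat a draw as normal with mean p and SD √(p(1−p)). Write Φ for the standard normal distribution function.

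| | p = 0.15 | p = 0.30 |
|---|---|---|
| SD | 0.357 | 0.458 |
| Share below 0: Φ(−p/SD) | 34% | 26% |
| Share above 1: 1−Φ((1−p)/SD) | 1% | 6% |
| Share rounded to 1 at 0.5: 1−Φ((0.5−p)/SD) | 16.3% | 33.1% |
| Shift among imputed values | +1.3 points | +3.1 points |
| Shift in the arm at 20% imputed | +0.3 points | +0.6 points |

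The difference between arms therefore moves by about 0.63 − 0.27 = 0.36 points.

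A simulation (1,000 replicates, 150 per arm, 20% missing completely at random, arm as the only predictor, 50 imputations) agrees:

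| Handling of missing values | I-ANBL | I-FV | Odds ratio |
|---|---|---|---|
| Binary imputation model | 29.9% | 15.1% | 2.40 |
| Normal model, unrounded | 29.9% | 15.0% | 2.40 |
| Normal model, rounded at 0.5 | 30.5% | 15.3% | 2.42 |

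**Quit attempts.** Treat a draw as normal with mean μ and SD s = √(kμ), where k is the ratio of variance to mean. The share of negative draws is Φ(−μ/s). If negatives are set to zero, the mean becomes μΦ(μ/s) + sφ(μ/s), with φ the normal density.

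| μ | k | Negative draws | Mean after zeroing | Rise among imputed | Rise overall at 20% |
|---|---|---|---|---|---|
| 1 | 1 | 15.9% | 1.083 | 8.3% | 1.7% |
| 1 | 2 | 24.0% | 1.200 | 20.0% | 4.0% |
| 1 | 3 | 28.2% | 1.303 | 30.3% | 6.1% |
| 2 | 1 | 7.9% | 2.050 | 2.5% | 0.5% |
| 2 | 2 | 15.9% | 2.167 | 8.3% | 1.7% |
| 2 | 3 | 20.7% | 2.286 | 14.3% | 2.9% |

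Over this grid about 8% to 28% of draws are negative. A mean of 3 with Poisson variance would give about 4%.

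**The case against.** The strongest reply is that the protocol never states a normal model. MCMC is a computing method and can be run with a binary or count imputation model, and the choice of model is often settled in a statistical analysis plan, which is not shown. That stands in part: normality is an inference from the EM-then-MCMC wording and the named software, and a later plan may already settle it. It does not dispose of the point, because the protocol goes beyond silence. It describes one procedure and then applies it by cross-reference to a different type of outcome.

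Three stronger readings are tempting, and the protocol does not support them.

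- A reader might infer that the imputed data could not be analysed at all. Rounding, or deriving abstinence from other imputed variables, gives usable values, and positive non-integer values can be fitted numerically in a Poisson model. What is missing is the stated conversion.
- A reader might extend the Poisson problem to cigarettes smoked. That outcome goes to a mixed model, which accepts continuous values, so the incompatibility does not arise.
- A reader might conclude that the primary result is at risk. Analyses (a) and (b) never produce a non-binary value, and in (c) the shift is small.

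**Conclusion.** The point holds as a minor one, conditional on the natural reading that a normal model is meant. On that reading the protocol pairs an imputation method with two outcome types it does not suit, and gives no conversion rule.

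For the primary endpoint only analysis (c) is touched. Under the protocol's rates and rounding at 0.5, the arms move by about 0.3 and 0.6 points and the simulated odds ratio from 2.40 to 2.42. The simulation used no covariates and data missing completely at random, so it shows the order of magnitude and not a bound.

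The case is stronger for quit attempts. Multiple imputation is the only dropout handling given there, negative draws have no valid Poisson likelihood, and zeroing them raises the overall mean by roughly 0.5% to 6%. That range rests wholly on the assumed mean and variance.

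**What to change.** In Primary Aim/Hypotheses, state that abstinence in analysis (c) is imputed with a logistic imputation model, either monotone logistic or fully conditional specification. In Secondary Aims/Hypotheses, replace the bare cross-reference for quit attempts with predictive mean matching or a count imputation model such as the negative binomial. Include treatment arm and baseline smoking as predictors in both. Confirm that the named software release offers the chosen option.

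The cost is a changed imputation statement and the matching program code. Sample size, data collection, and analyses (a) and (b) stay as they are. If a statistical analysis plan already specifies such models, a reference to it is enough.
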